## 7.2 Methods and Timing for Assessing, Recording, and Analyzing Safety Parameters

Patients on insulin and sulfonylureas have a higher risk of hypoglycemia with dapagliflozin and GLP-1 agonists may influence cognitive outcomes and will be excluded. Ketoacidosis has been reported with dapagliflozin in type 1 diabetes and patients with type 1 diabetes will be excluded from the study. Since the efficacy of dapagliflozin is dependent on renal function, we will exclude individuals with an eGFR below 45 ml/min/1.73m2.

In addition, participant safety will be ensured through education, clinical assessment, and laboratory testing.

Education: Dapagliflozin has been associated with reduced blood volume.. Participants will thus be educated on symptoms of volume depletion such as lethargy, fatigue or dizziness. Before initiating dapagliflozin, volume status will be assessed and suspected hypovolemia will be corrected through increased oral intake.

For early diagnosis of infectious AEs associated with dapagliflozin, participants will also be educated on the signs and symptoms of urinary tract infections, vaginal yeast infections, and balanitis, such as dysuria, hematuria, increased urinary frequency, tenderness, pruritus or erythema in the genital areas.

Clinical assessment: Assessment of fluid status with vitals and physical exam will be performed at baseline visit before initiating dapagliflozin. Symptoms of hypovolemia will be assessed at all visits during therapy. Sitting and standing blood pressure and body weight will be assessed at every visit. At each visit, participants will be evaluated and provide a urine sample for signs and symptom of urinary tract or genital infections, and treated appropriately as indicated. Participants will be encouraged to increase fluid intake in those with evidence of hypovolemia.

Laboratory testing: Safety laboratory testing will be conducted at baseline, week 1, week 4, week 8, week 12, and week 14 to monitor for acute kidney injury, hypoglycemia, dehydration, infections, ketoacidosis, and hypo- or hyperphosphatemia. Laboratory tests included will be: complete blood count with differential (hemoglobin, hematocrit, red blood cell count, white blood cell count, platelet count, neutrophil count, lymphocyte count, monocyte count, eosinophil count, basophil count), comprehensive metabolic panel (blood urea nitrogen, creatinine, eGFR, albumin, calcium, bicarbonate, glucose, potassium, sodium, total bilirubin, total protein, alanine aminotransferase, alkaline phosphatase, and aspartate aminotransferase) and serum phosphorus. Fasting lipid panel will be checked at baseline and week 12 to monitor cholesterol including LDL-C.

In addition to these labs, a safety urinalysis will be performed at every visit.

Weight Loss: Body weight will be assessed at baseline, week 1, week 4, week 8, week 12, and week 14/end-of-study. If total weight loss reaches 5% of total body weight compared to baseline and is associated with any concomitant clinical symptoms (fatigue, weakness, reports of cognitive worsening, etc), the study drug will be held or stopped per the judgment of the investigator.

Temporary interruption or cessation of the investigational product (IP) will be considered for individuals per the judgment of the investigator for those who develop orthostatic hypotension or other symptoms of volume depletion, renal impairment, weight loss greater than 5% total body weight at baseline, ketoacidosis or other AEs judged to be related to the study drug.

Overdose: An overdose is defined as a patient receiving a dose of IP in excess of that specified in the Investigator's Brochure, unless otherwise specified in this protocol.

Any overdose of a study patient with the investigational product., with associated AEs/SAEs, is required to be reported within 24 hours of knowledge of the event to the sponsor and AstraZeneca Patient Safety or designee using the designated Safety e-mailbox (see Section 1.6 or contact information). If the overdose results in an AE, the AE must also be recorded as an AE. Overdose does not automatically make an AE serious, but if the consequences of the overdose are serious, for example death or hospitalization, the event is serious and must be recorded and reported as an SAE (see Section 1.6). The investigator will use clinical judgment to treat any overdose.

## 7.3 Adverse Events and Serious Adverse Events

An **adverse event (AE)** is generally defined as any unfavorable and unintended diagnosis, symptom, sign (including an abnormal laboratory finding), syndrome or disease, which occurs during the study, having been absent at baseline, or if present at baseline, appears to worsen. Adverse events are to be recording regardless of their relationship to the study intervention.

A serious adverse event (SAE) is generally defined as any untoward medical occurrence, occurring after the signing of the informed consent through the follow-up period that fulfils one or more of the following criteria: that results in death, is life threatening, requires hospitalization or prolongation of existing hospitalization, results in persistent or significant disability/incapacity, , an important medical event that may jeopardize the patient or may require medical intervention to prevent one of the outcomes listed above.. or is a congenital anomaly.

All SAEs will be reported, whether or not considered causally related to the IP, or to the study procedure(s). All SAEs will be recorded in the CRF. The causality of SAEs (their relationship to all study treatment/procedures) will be assessed by the investigator(s) and communicated to AstraZeneca.

AEs and SAEs will be collected from the time of informed consent until end of study (week 14).

The following variables will be collected for each AE;

- AE term, using the diagnosis if known, or signs or symptoms when diagnosis is not known
- The date when the AE started and stopped
- Maximum intensity (mild, moderate or severe)
- Whether the AE is serious or not
- Investigator causality rating against the Investigational Product (yes or no)
- Action taken with regard to investigational product
- Outcome.
- In addition, the following variables will be collected for SAEs:

- Date AE met criteria for serious AE
- Date Investigator became aware of serious AE
- Criterion that classifies AE as serious
- Date of hospitalization
- Date of discharge
- Probable cause of death
- Date of death
- Autopsy performed
- Causality assessment in relation to Study procedure(s)
- Description of AE.

## 7.4 Reporting Procedures

All AEs (related or unrelated to the study intervention) will be reported quarterly to the Safety Officer for review. A summary of these quarterly reports will be provided to the KU IRB on an annual basis. In addition, expedited reporting to the KU IRB will follow IRB guidelines.

Serious Adverse events i.e. Suspected, unexpected, serious, adverse, reaction (SUSAR) will also be reported to the FDA in an expedited fashion, following these guidelines:

- Within 7 calendar days
  - Any adverse event that is:
    - associated with the use of the study drug
    - unexpected,
    - fatal or life-threatening, and

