#### **Interventions and Duration**

Participants will be randomized (2:1 ratio) to either dapagliflozin 10mg a day vs matching placebo for a treatment duration of 12 weeks. The total study duration for participants will be will be up to 18 weeks. In-person screening and baseline assessments will occur within a 4-week time-window prior to randomization. Study drug (or placebo) will begin at randomization (time 0) and in person assessments will occur at weeks 1, 4, 8, and 12 weeks (when study drug is stopped) and an end of study visit at 14 weeks.

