#### 6.2.3.2 Week 12 (Visit 6) Safety and Other Outcome Assessments

Safety assessments and outcome measures will be completed after 12 weeks (Visit 6) of intervention, including the following:

- Review of concurrent medications
- Review/check for any adverse events
- Vital signs
- Body weight
- Physical and neurological examination
- Blood and urine collection for clinical safety laboratory tests and biomarker outcomes
- Urine collection for NAA levels
- Cognitive battery
- MRI/MRS
- FDG PET
- Metabolic assessments
- Study medication compliance check

The Week 12 (Visit 6) procedures may be completed in any order depending on ancillary facility scheduling availability and participant convenience, but all Week 12 procedures will be completed while the participant continues to take the study drug (+/- 7 days of the 12-week time point). As a result, participants may take the study drug for up to 13 weeks in duration.

A description of each procedure listed can be found above under Screening or Baseline Visit procedures.

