## 7.6 Safety Monitoring

A safety officer with expertise in clinical trials and in use of SGLT2 inhibitors will be appointed to monitor drug safety. The safety monitor will review AE's and study data quarterly and advise the study team on additional monitoring if needed or need for termination of study in case of unexpected serious AE's.

The study may be stopped if, in the judgment of the safety officer, study participants are placed at undue risk because of clinically significant findings that are assessed to be causally related to the study drug.

Safety measures to be reviewed by the safety officer include, laboratory abnormalities, AEs, and discontinuations. These safety measures will be carefully collected and recorded by the study team as they have extensive prior experience and expertise with these procedures.

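### Sections 7.4 and 7.6 bring serious adverse events to the safety officer only on a quarterly cycle, with no expedited route to the person whose judgment can stop the study

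*Combined protocol and SAP*

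**What the plan says.** Section 7.4 sets the flow of events to the officer: "All AEs (related or unrelated to the study intervention) will be reported quarterly to the Safety Officer for review". Section 7.6 sets the same rhythm for the officer's own work: "The safety monitor will review AE's and study data quarterly and advise the study team on additional monitoring if needed". That sentence goes on to ask for advice on the "need for termination of study in case of unexpected serious AE's". The next paragraph of 7.6 adds the stopping authority: "The study may be stopped if, in the judgment of the safety officer, study participants are placed at undue risk", where the findings are clinically significant and judged to be caused by the drug.

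The quicker or event-driven routes are these:

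- Section 7.4: expedited reporting to the IRB under its own guidelines.
- Section 7.4: SUSARs to the FDA in 7 calendar days if fatal or life-threatening, otherwise 15.
- Section 7.4: SAEs, copies of FDA reports and SAE-related unblinding to AstraZeneca.
- Section 7.2 (Overdose): overdoses with associated events to the sponsor and AstraZeneca in 24 hours.

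The safety officer is on none of these lists. Section 9.3 plans no interim analysis and no stopping rule. Section 11.4 lets the IRB, FDA and other government bodies discontinue the study at any time.

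**The concern.** The officer's role and the officer's information do not match. Section 7.6 expects a response to unexpected serious events, which depends on hearing of them soon. Section 7.4 supplies them on a quarterly schedule. With no statistical stopping rule and no data monitoring board described, the officer is the only study-level safety reviewer that the protocol itself appoints.

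The consequence is an odd order of knowledge. The FDA and the drug supplier can hold a report of an unexpected serious reaction weeks before the person appointed to judge whether the study should go on. Meanwhile enrolled participants continue on study drug and new ones start.

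**Working it through.** The plan gives no figure for this delay, so there is none to reproduce. The check has two parts: the recipients of each report, and the length of the wait.

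**Recipients.** Section 7.3 records for each adverse event whether it is serious, so SAEs are a subset of the events that 7.4 sends quarterly. Sections 7.2 to 7.6, 8, 9.3, 10.3.4, 10.3.5 and 11.4 contain no other route to the officer. Section 7.2 refers to a Section 1.6 for SAE reporting. The text available has Sections 1.1 to 1.3 only, so nothing can be concluded from that reference either way.

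**Inputs.**

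- Review interval: quarterly (7.4 and 7.6), taken as q = 365.25 / 4 = 91.3 days = 13.04 weeks. Calendar quarters of 90 to 92 days give 12.86 to 13.14 weeks.
- Time on drug: "a treatment duration of 12 weeks" (Précis, Interventions and Duration), d = 84 days. Section 6.2.3.2 adds that "participants may take the study drug for up to 13 weeks in duration", so d = 91 days at most.
- Assumptions: event times are uniform, review dates are unrelated to a participant's start date, and the officer sees the event on the review date. Time to prepare the report would add to the wait.

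**Wait from event to review.**

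- Longest wait: q = 91.3 days, about 13 weeks.
- Mean wait: q / 2 = 91.3 / 2 = 45.7 days, about 46 days.
- Share waiting more than 7 days: 1 − 7 / 91.3 = 92%.
- Share waiting more than 15 days: 1 − 15 / 91.3 = 84%.

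The 7- and 15-day marks are the FDA limits in 7.4. They apply only to qualifying events and serve here as a yardstick.

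**Wait against treatment length.**

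| Quantity | d = 84 days | d = 91 days |
|---|---|---|
| q − d | 7.3 days | 0.3 day |
| Participants with no review while on drug, (q − d) / q | 8.0% | 0.3% |
| On-treatment events whose next review precedes that participant's last dose, d / (2q) | 46% | 50% |

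So a quarter is about as long as treatment, and about 92% of participants on 84 days have some review during dosing. For an event on treatment, however, the next review comes after that participant's dosing has ended in about half of cases.

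**New starts during one interval.** Accrual time is not stated. If 48 participants accrue evenly over an assumed 12, 24 or 36 months, 48 × 3 / months gives 12, 6 or 4 randomized per quarter. At 2:1 (Section 9.2), two-thirds of these receive dapagliflozin: 8, 4 or 2.7. These are counts for the longest wait. At the mean wait, half a quarter, they are 4, 2 or 1.3.

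**The case against.** The strongest reply is that independent oversight does not hang on the officer. The IRB receives expedited reports, the FDA receives SUSARs in 7 or 15 days, and Section 11.4 lets both discontinue the study. Sections 7.2 and 8 let the investigator hold or stop drug for an individual. This stands. A reader might infer that the officer is the only independent safety check, and the documents contradict that. What remains is that the reviewer appointed for this study, with SGLT2 expertise, is left off the fast routes.

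A reader might also infer that the review interval outlasts treatment, so that participants finish before anyone looks. The documents do not support this. With up to 13 weeks on drug, a quarter is only about as long as treatment, a 90-day quarter is shorter, and most participants have a review while dosing.

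It is also fair to say that 7.4 sets a schedule without forbidding earlier contact, and that the 7.6 wording on unexpected serious events could be read as event-driven. Staff may well call the officer. But no sentence requires it or sets a time, while the other recipients have written routes.

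Finally, this is a 48-person, single-site pilot of an approved drug, with safety laboratory tests and event review at every visit. That limits the exposure at stake. It does not explain why the officer should hear last.

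**Conclusion.** The point holds as a gap in the reporting route. As written, the officer can learn of an SAE up to about 13 weeks after it occurs, and about 46 days after it on average. The 13-week figure follows from the quarterly schedule alone; the mean rests on uniform event times and on review dates unrelated to the event. Both assume that staff do no more than the text requires.

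The number of participants who start dapagliflozin during one full interval, about 8 to 3, rests on an assumed accrual time of 12 to 36 months and is only indicative. A figure of 12 to 4 would count both arms.

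No estimate of the primary outcome is affected. The case for change rests on safety oversight and on consistency between 7.4 and 7.6, and the remedy is nearly free.

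**What to change.** In Section 7.4:

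- Copy each SAE report to the safety officer when it is sent to AstraZeneca, within a stated time limit. The limit must be written down for all SAEs, because 7.4 gives no deadline for sending AstraZeneca those that need no expedited FDA report. Without one, copies of those reports would have no deadline either.
- Copy each SUSAR to the officer on the existing 7- or 15-day FDA clock.
- Keep all adverse events, SAEs included, in the quarterly report. Restricting it to non-serious events would take SAEs out of the officer's cumulative review and out of the annual IRB summary built from it.

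In Section 7.6, state that the officer reviews SAEs on receipt as well as reviewing all data quarterly, so that the two sections agree.

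The cost is a few sentences and one more recipient for reports that are already written. No visit, endpoint or analysis changes.

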#### • Within 15 calendar days

Any adverse event that is:

- associated with the use of the study drug,
- unexpected, and
- serious, but not fatal or life-threatening
- a previous adverse event that was not initially deemed reportable but is later found to fit the criteria for reporting (reporting within 15 calendar days from when event was deemed reportable).

The investigator must inform the FDA, e.g. via a MedWatch form, of any serious or unexpected adverse events that occur in accordance with the reporting obligations of 21 CFR 312.32. A copy of the MedWatch report must be emailed concurrently to AstraZeneca (TCS vendor) at the time the event is reported to the FDA. It is the responsibility of the sponsor to compile all necessary information and ensure that the FDA receives a report according to the FDA reporting requirement timelines and to ensure that these reports are also submitted to AstraZeneca at the same time.

- Sponsor must also indicate, the causality of events in relation to all study medications and if the SAE is related to disease progression, as determined by the principal investigator.
- Send SAE report and accompanying cover page by way of email to AstraZeneca's designated mailbox: [contact]

- If a non-serious AE becomes serious, this and other relevant follow-up information must also be provided to AstraZeneca and the FDA.
- Serious adverse events that do not require expedited reporting to the FDA still need to be reported to AstraZeneca.
- The investigator will report to AstraZeneca any unblinding that occurs due to critical patient safety concern related to an SAE.

#### 7.5 Follow-up for Adverse Events

All AEs reported during time of study, will be followed by the study team up to 14 days after last dose administration. Any unresolved AEs considered probably study drug related, will be followed up by the study team until the AE has resolved or is considered stable.

## 7.6 Safety Monitoring

A safety officer with expertise in clinical trials and in use of SGLT2 inhibitors will be appointed to monitor drug safety. The safety monitor will review AE's and study data quarterly and advise the study team on additional monitoring if needed or need for termination of study in case of unexpected serious AE's.

The study may be stopped if, in the judgment of the safety officer, study participants are placed at undue risk because of clinically significant findings that are assessed to be causally related to the study drug.

Safety measures to be reviewed by the safety officer include, laboratory abnormalities, AEs, and discontinuations. These safety measures will be carefully collected and recorded by the study team as they have extensive prior experience and expertise with these procedures.

## 8 INTERVENTION DISCONTINUATION

Screening failures are participants who do not fulfill the eligibility criteria for the study, and therefore must not be randomized. Participants may be discontinued from investigational product (IP) in the following situations:

- Participant withdrawal of consent. The participant is at any time free to discontinue treatment, without prejudice to further treatment.
- Adverse Event. The investigator may elect to discontinue the participant from treatment if he feels it is in the best interest of the participant.
- Significant noncompliance (<80% medication compliance) on the part of the participant with the study protocol

At any time, participants are free to discontinue IP or withdraw from the study (i.e. IP and assessments), without prejudice to further treatment. A participant that decides to discontinue IP will always be asked about the reason(s) and the presence of any adverse events (AEs). If the participant is discontinued from IP, the participant will be asked to

return to site for an optional safety follow-up visit. The study drugs should be returned by the participant at this visit.

If a participant withdraws from participation in the study, then his/her enrolment/randomization code will not be reused. Withdrawn participants will not be replaced. All data available for the participant at the time of discontinuation of follow-up will be recorded. All reasons for discontinuation of treatment will be documented.

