# 7 SAFETY ASSESSMENTS

## 7.1 Dapagliflozin Safety Profile

Randomized clinical trials and post-marketing data have found the dapagliflozin is associated with potential adverse effects including hypoglycemia, laboratory increases in hematocrit, serum phosphorus and LDL-C, ketoacidosis, urinary tract infections, genital infections, and weight loss. When used as monotherapy, the risk for hypoglycemia was low and similar to those taking placebo. Higher rates of hypoglycemia were seen when dapagliflozin was used in combination with sulfonylurea or insulin therapy. A small reduction in blood pressure has been seen in patients treated with dapagliflozin.

Hypoglycemia: Dapagliflozin promotes glycosuria. Hypoglycemia has been reported with dapagliflozin, especially with dapagliflozin as an add-on to sulfonylureas or insulin. In studies with dapagliflozin used as monotherapy, or as add-on to metformin or pioglitazone there were no reported major episodes of hypoglycemia in up to 102 weeks (ref).

Increase in hematocrit and serum phosphorus: Other AEs reported with dapagliflozin include an increased hematocrit (+2.3% compared to Baseline versus -0.33% in the placebo group) and serum inorganic phosphorus (+0.13 mg/dL vs -0.04 mg/dL in the placebo group).

Ketoacidosis: Ketoacidosis has been reported in post-marketing studies in patients with type 1 and type 2 diabetes.

Infections: Treatment with dapagliflozin increases the risk for urinary tract and genital infections. The most frequently reported genital infections are vulvovaginal mycotic infections in females, and balanitis in males. Most patients responded to an initial course of standard treatment, and these infections rarely caused discontinuation from the study.

Weight loss: Urinary glucose excretion induced by dapagliflozin is associate with caloric loss and reduction in weight. The majority of weight reduction is body-fat loss (rather than lean tissue) and fluid loss. In a 24 week placebo controlled study in type 2 diabetes comparing dapagliflozin in combination with antidiabetic agents, body weight dropped 2.26 kg in the dapagliflozin group vs 0.72kg in placebo. Though weight loss is beneficial in diabetes patients, weight loss in patients with AD is often a poor prognostic sign and

associated with greater clinical progression. No studies have demonstrated that the loss of body fat rather than lean tissue is detrimental.

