#### 9.5 Data Analyses

Unless otherwise specified, all efficacy analyses will be carried out on all subjects enrolled. Continuous variables will be summarized (using number of participants, mean, standard deviation, and percentiles) by treatment group and visit. For baseline, all end-ofstudy measurements, the changes, or relative changes from baseline will be presented by treatment group for all efficacy variables to be analyzed. Categorical variables will be summarized, by treatment group, using frequency count and the percentage of participants in each category. This will facilitate assessment for independence in these baseline measures across treatment groups, which we anticipate given treatment will be allocated at random. (Notably, this inference of independence is equivalent to testing for no difference in proportional distributions across treatment groups.)

The primary objective is estimation, so we will generate 95% confidence intervals for "adjusted" treatment means and their differences based on the formulas analogous to an analysis of covariance (ANCOVA)/ordinary least squares (OLS) regression model hypothesis testing procedure. For these models we will use the baseline measure as a covariate, including assigned treatment as a fixed effect, and change from baseline measure (i.e., follow-up minus baseline) as the response/outcome measure. To deem the adequacy of normal distribution quantiles for confidence interval estimation we will carry out the residual analyses to assess the assumptions of that test for each measure. In the event that the residual diagnostics (including residual vs. predicted value plots, quantilequantile plots, etc.) do not conform to the underlying normality and other assumptions of this test, we will revert to nonparametric rank-based approach using ANCOVA as described above with ranks used instead for the response to derive model-based p-values. For categorical measures, we will use confidence intervals based on the Wald estimate of the standard error in comparisons of proportions between assigned treatment for dichotomous responses/outcomes if the expected cell counts (under the hypothesis of independence) for corresponding contingency tables are at least five in most (>80%) cells. If the expected cell counts are not sufficiently large, we will instead estimate using exact, Clopper-Pearson confidence intervals.

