To assess scan-rescan reliability for NAA on the 12 subjects, we will estimate the variance in the difference scores between each of these 12 subjects' pre-randomization MRI/MRS scans. This will provide information on intra-individual scan-to-scan variation for consideration as we interpret differences (time one minus time two) estimated between treatment groups.

As only pre- and post-treatment measures are obtained, subjects missing post-treatment follow-up measures will be excluded from these analyses.

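### The plan does not call for the Week 12 MRS once study drug is stopped, so the primary NAA estimate may exclude participants because of a post-randomisation event

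*Combined protocol and SAP*

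**What the plan says.** Section 8 allows study drug to be stopped by participant choice, for an adverse event, or for compliance below 80%. Section 7.2 adds safety grounds (volume depletion, renal impairment, weight loss above 5%, ketoacidosis, other related events): "Temporary interruption or cessation of the investigational product (IP) will be considered for individuals per the judgment of the investigator".

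Three provisions bear on what happens next:

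- Section 8: a participant discontinued from drug is asked to "return to site for an optional safety follow-up visit" and to return the tablets there. No outcome assessment is mentioned.
- Section 6.2.3.2: "all Week 12 procedures will be completed while the participant continues to take the study drug", within 7 days either side of Week 12. The list of procedures includes MRI/MRS.
- Section 9.5: because outcomes are measured only before and after treatment, "subjects missing post-treatment follow-up measures will be excluded from these analyses".

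Two provisions point the other way. Section 8 says "participants are free to discontinue IP or withdraw from the study (i.e. IP and assessments"), so stopping drug and leaving the study are different events. Section 5.4 keeps non-compliant participants in the study.

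The Schedule of Evaluations (section 6.0) has no column for an off-drug or early-termination outcome visit.

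**The concern.** The primary objective is to estimate the effect on cerebral NAA, and there is one post-baseline scan. A participant who stops drug and is not scanned at Week 12 has no primary outcome and leaves the analysis. The comparison is then between those in each arm who were still on drug at Week 12, which randomisation no longer protects. The confidence interval allows for the smaller numbers but not for the selection. A scan missed at Week 12 cannot be recovered at analysis. Section 9.2 says the results will inform power calculations for later trials, so a selected estimate would carry forward.

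Stops could be uneven between arms, because several section 7.2 grounds are known effects of the drug.

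**Working it through.** **Reading the provisions together.** Take a participant who stops drug at Week 5 for an adverse event and does not withdraw consent.

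- Section 8 offers an optional safety visit. Such an offer would have little purpose if all scheduled visits were understood to continue.
- Section 6.2.3.2 tells staff how to time Week 12 procedures for someone still dosing. It is silent on someone already off drug.
- If no scan is done, section 9.5 removes the participant. If a scan is done, nothing in 9.5 removes the participant, and the model uses assigned treatment.

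The outcome therefore turns on whether staff arrange a scan that the plan does not ask for.

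**The plan's own figure.** Section 9.2 gives 32 and 16 randomised, 27 and 13 after attrition, and a 95% half-width of about 0.69 SD. The formula is t(0.975, n1+n2−2) × √(1/n1 + 1/n2).

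- 27 and 13: 2.024 × √(1/27 + 1/13) = 2.024 × 0.3376 = 0.683 SD. With the section 9.2 SD of 0.2 for NAA/Cr change, this is 0.137. Both agree with the plan (0.69 and 0.14).
- 32 and 16: 2.013 × √(1/32 + 1/16) = 2.013 × 0.3062 = 0.616 SD.
- Keeping every scan would narrow the interval by at most 1 − 0.616/0.683 = 9.8%. Precision is not the main issue.

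**Possible shift from selection.** All inputs here are assumed. Let mA of 32 active and mP of 16 placebo participants be lost, and let their mean NAA change differ from that of those retained by d SD, with the same d in both arms. The shift in the estimated difference is |mA/32 − mP/16| × d. Planned attrition gives mA = 32 − 27 = 5 and mP = 16 − 13 = 3.

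| Lost (active, placebo) | d (SD) | Shift (SD) | Share of 0.683 |
|---|---|---|---|
| 5, 3 | 0.5 | 0.03125 × 0.5 = 0.016 | 2.3% |
| 5, 3 | 1.0 | 0.03125 × 1.0 = 0.031 | 4.6% |
| 1, 0 | 0.5 | 0.03125 × 0.5 = 0.016 | 2.3% |
| 5, 0 | 0.5 | 0.15625 × 0.5 = 0.078 | 11.4% |
| 5, 0 | 1.0 | 0.15625 × 1.0 = 0.156 | 22.9% |

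On the NAA/Cr scale (SD 0.2) the table runs from 0.003 to 0.031. If those lost in the two arms differed in opposite directions, the terms would add: 5/32 × 0.5 + 3/16 × 0.5 = 0.172 SD. Nothing in the documents points to that pattern.

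**Dilution if those off drug are scanned.** If they keep no residual effect, the as-randomised effect is 31/32 = 97% of the on-drug effect with 1 of 32 active participants off drug, and 27/32 = 84% with 5 off drug.

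**The case against.** The strongest reply is that the plan already leans towards follow-up. Section 8 ties the end of assessments to withdrawal only, section 5.4 retains non-compliers, exclusion in 9.5 depends on a missing measure rather than on drug status, and the model uses assigned treatment. The 6.2.3.2 sentence is mainly a dosing rule: the next sentence draws from it that treatment may last up to 13 weeks. All of this stands, and it rules out reading the plan as forbidding the scan. It does not supply the missing instruction.

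Three further inferences a reader might draw are not supported:

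- *That section 9.5 contradicts itself.* It says "all efficacy analyses will be carried out on all subjects enrolled", but that sentence opens by allowing for exceptions specified elsewhere, and the exclusion of missing outcomes is one.
- *That the weight data show uneven stopping.* Section 7.1 reports that "body weight dropped 2.26 kg in the dapagliflozin group vs 0.72kg in placebo", but over 24 weeks in type 2 diabetes. The section 7.2 threshold is 5% with investigator judgment. A loss of 2.26 kg is 5% only at 2.26/0.05 = 45.2 kg, which at the BMI floor of 23 means a height of √(45.2/23) = 1.40 m. Individuals vary, but a mean difference does not show stops at that threshold. On infections, section 7.1 says "these infections rarely caused discontinuation from the study".
- *That a shift near 23% of the half-width is to be expected.* It needs every planned active loss to be a drug stop, a full 1 SD difference, and none of the three planned placebo losses.

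It can also be said that the objective concerns 12 weeks of daily dosing, so an on-drug estimate may be what is wanted. That is a fair point about the target. A completers-only comparison can still be biased for that target, and a supplementary on-drug analysis would address the same question. Finally, the attrition allowance covers lost precision, not who is lost, and some attrition will be true withdrawals that no wording can recover.

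**Conclusion.** The point holds as an omission. Read together, sections 8, 6.2.3.2 and 9.5 leave the Week 12 scan of a participant off drug neither forbidden nor requested. That it would usually be missed is a judgment from the optional safety visit and the absence of any off-drug outcome visit, not something the plan states.

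The size and direction of any bias are unknown, since the documents give neither stop rates by arm nor NAA values for those who stop. Under the assumed differences of 0.5 to 1.0 SD, it is about 2% to 5% of the half-width if planned losses occur in both arms with the same difference. With loss on active only, it reaches about 23% when all five planned active losses are drug stops differing by 1 SD. The sample-size figure in section 9.2 is sound and is not in question. This is a minor to moderate concern, worth acting on because the remedy is cheap and the data cannot be collected later.

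**What to change.** 1. Section 8: state that a participant who stops study drug stays in the study and is asked to complete at least the Week 12 MRI/MRS, and the other outcome assessments where safe and acceptable, 12 weeks (within 7 days either side) after randomisation, unless consent to assessments is withdrawn.
2. Section 6.2.3.2: limit the on-drug wording to participants still taking study drug.
3. Section 9.5: state that these participants are analysed in their assigned arm, using the assigned-treatment term already in the model, with an analysis of those on drug at Week 12 as a supplement.

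The compliance ground for stopping drug in section 8 can stay.

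Cost: wording in three sections, no added participants, and no procedure beyond the Week 12 assessments already scheduled. The consent form is not among the documents reviewed and needs a matching line only if it lacks one. The downside is the dilution shown in the working (84% of the on-drug effect with 5 of 32 off drug and no residual effect), which the supplementary analysis helps readers to interpret.
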